8.1.2. Grading of adverse events

All AEs in the trial will be graded according to the Common Terminology Criteria for Adverse Events (CTCAE), version 5.0. NCI CTCAE is originally a standard term designed to report AEs that occur during cancer clinical trials. CTCAE contains a grading scale representing the severity of an event, from grade 1 to grade 5.

- Grade 1: mild; asymptomatic or mild symptoms; clinically or diagnostically observed; no intervention required.
- Grade 2: moderate; indicating minimal local non-invasive intervention; instrumental activity of daily living corresponding to age is restricted (applicable to AEs involving metabolism, nutrition and immunity).
- Grade 3: a severe or medically important event, but not immediately life-threatening; resulting in hospitalization or prolonged hospital stay; disability; restriction of self-care activity of daily living.
- Grade 4: a life-threatening consequence; indicating emergency treatment.
- Grade 5: deaths related to AE.

Note: The CTCAE provides specific grading scales for abnormalities shown in a laboratory test. Grade 4 abnormality shown by a laboratory test does not automatically represent a life-threatening event. An abnormal result shown by a laboratory test still needs to be evaluated before it is determined whether such result is an AE or not.

The safety data from the ongoing trial will be submitted to the medical monitor for review.

8.1.3. Determination of causality between adverse events and investigational product

According to the categories below, a causal relationship between the AE and investigational

product will be evaluated as definitely related, possibly related, unlikely related and not related. A drug-related AE is defined as an AE that is definitely related or possibly related.

- Definitely related: the type of an AE has been identified as a known type of reaction to the investigational product and cannot be explained by other reasons, such as concomitant medications or comorbidities. The time of occurrence of an event strongly suggests a causal relationship (e.g., based on the outcome following drug withdrawal and restart).
- Possibly related: an AE occurs with a reasonable time sequence to the administration of
 the investigational product, indicating that the occurrence of such AE may be caused by
 the investigational product. The possibility that the AE is caused by other factors, such
 as a concomitant medication or comorbidity, cannot be ruled out. The drug is not
 withdrawn or re-administered orally.
- Unlikely related: no evidence shows a causal relationship between the occurrence of the event and the investigational product. The occurrence of the AE is more possibly related to other factors, such as a concomitant medication or comorbidity. There is a negative or ambiguous reaction after drug withdrawal. However, the relation between the drug and the event cannot be ruled out.
- Not related: the subject does not take the investigational product; the occurrence of the AE is not consistent with the time sequence of administration; or such event can be caused by other significant factors.

The investigator should re-assess the causal relationship based on subsequent follow-up information and update the corresponding AE/SAE report as required.

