5.4.4. Criteria for termination of treatment or early withdrawal of subjects

Subjects should be encouraged to complete the study, but they are allowed to voluntarily withdraw from the study at any time during its conduct. The investigator should provide written statements of the withdrawal of subjects from the study. Primary reasons why subjects terminate or withdraw from the study or discontinue the investigational product should be recorded in the eCRF according to the following classifications.

1) Adverse events (AEs)

The Subject has experienced an AE that requires early termination because continued participation imposes an unacceptable risk to the subject's health or the subject is unwilling to continue because of the AE.

• Liver function test (LFT) abnormalities

The investigational product should be discontinued immediately, and appropriate clinical follow-up should be performed (including repeated laboratory tests until the subject's laboratory measurements returns to normal or baseline, please refer to Section 7.5), if the following circumstances occur at any time during study medication treatment:

- ALT or AST $> 8 \times ULN$, or
- ALT or AST > 5 \times ULN and a re test > 5 \times ULN, or
- ALT or AST > 3 \times ULN and elevated total bilirubin > 2 \times ULN, or international normalized ratio (INR) > 1.5, or
- ALT or AST > 3 ×ULN with fatigue, nausea, vomiting, right upper quadrant pain or tenderness, fever and rashes.

• Decrease in pulmonary function

If the subject's pulmonary function test results (FEV₁ and/or FVC) fall below 50% of the predicted values, treatment should be discontinued immediately, and appropriate clinical follow-up should be performed (please refer to Section 7.5).

Macular edema

All subjects diagnosed with macular edema must discontinue the investigational product (see Section 7.5).

2) Significant protocol deviation at the time of enrollment or during the study

The discovery post randomization that the subject fails to meet protocol entry criteria or does not adhere to protocol requirements, and continued participation in the study may poses unacceptable risk to the subject's health.

3) Lost to follow-up

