8.2.2. Reporting and follow-up of serious adverse events

SAEs will be collected after subjects sign the informed consent form and throughout the entire study, i.e., until 28 days after the last dose of investigational product.

For any SAEs in the study, whether related to investigational product or not, the investigator should provide timely emergency treatment, and must immediately (within a maximum of 24 hours after becoming aware of the event) inform the sponsor or its designee, and complete the SAE Report Form following specific completion instructions. In the meantime, the investigator should record the SAE in the medical records and eCRF in a timely manner. The investigator must provide causality assessment when reporting SAEs.

Investigator safety reports must be prepared for suspected unexpected serious adverse reactions (SUSARs) according to local regulatory requirements and Sponsor policy and forwarded to Investigators as necessary.

For all SAEs, the investigator needs to conduct follow-up until subjects recover, have stable condition or returns to baseline condition, and provide detailed follow-up information. The timeline and procedure for the follow-up report are the same as the initial report, namely, the investigator should report any follow-up information about the SAEs within 24 hours after awareness.

Regarding follow-up:

- The investigator needs to take appropriate measures to protect the safety of the subject, and it is particularly required that each subject with AEs (abnormal clinical signs, laboratory test results, or others) should be followed up until he/she returns to normal or has stable condition.
- Subjects experiencing SAEs must be followed up until they recover clinically, return to normal or have stable condition. This may require follow-up visits after subjects leave the study and require additional investigation by sponsor.

The original report in written form should be presented in time with details, including a copy of the hospital medical record, a discharge summary, autopsy report (if applicable) and other necessary documents.

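### Read literally, the *Possibly related* definition excludes adverse events after which the drug was permanently withdrawn, so the drug-related TEAE tables may under-classify them

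*Protocol*

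**What the plan says.** Protocol Section 8.1.3 has four categories: definitely, possibly, unlikely and not related. The first two make up the drug-related group: "A drug-related AE is defined as an AE that is definitely related or possibly related".

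- Under *Definitely related*, the event has to be of an established kind with no other explanation: "the type of an AE has been identified as a known type of reaction to the investigational product and cannot be explained by other reasons". Timing must also point strongly to the drug, and the text gives an example: "e.g., based on the outcome following drug withdrawal and restart".
- *Possibly related*: reasonable timing, other causes not ruled out, and then "The drug is not withdrawn or re-administered orally".
- *Unlikely related*: no evidence of causality, other factors more likely, and "There is a negative or ambiguous reaction after drug withdrawal".
- *Not related*: drug not taken, timing inconsistent, or another significant factor can account for the event.

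The section also tells the investigator to re-assess causality as follow-up information arrives.

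SAP Section 15.1.1.2 uses the same scale (shortening the top label to *Related*), counts the top two categories as related, and counts a missing relationship as related. It does not redefine *Possibly related*.

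**The concern.** Improvement after a drug is stopped is ordinary evidence in favour of a causal link. Here the category that should hold most suspected events carries a condition that permanent withdrawal fails. The only remaining drug-related category is much narrower.

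The protocol itself requires withdrawal for some of its key safety events. Section 5.4.4 says of the listed liver-test thresholds "The investigational product should be discontinued immediately, and appropriate clinical follow-up should be performed". It also requires stopping for FEV1 or FVC below 50% of predicted and for macular edema. For these events *Possibly related*, read literally, is closed by the protocol's own stopping rules.

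Relationship to study drug is part of the secondary safety endpoint (Protocol Section 4). Drug-related TEAEs are tabulated at the primary analysis (SAP Section 4.2), and all TEAEs are broken down by relationship (SAP Section 15.1.1). If sites apply the wording literally, those tables are least reliable for the events that ended treatment. If only some sites do, relatedness is scored inconsistently across the four countries.

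**Working it through.** The plan gives no figure to reproduce. The check applies the wording of Section 8.1.3 to every combination of the features it names, assuming plausible timing and a subject who took the drug.

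**Step 1: the sentence itself.** It can mean neither withdrawn nor re-administered, or it can mean either not withdrawn or else re-administered. Permanent withdrawal fails both readings, so the result does not depend on the parse.

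**Step 2: two features, 2 × 2 = 4 combinations.** The features are type of event (known or new) and other cause (excluded or not). *Definitely related* needs known type and other cause excluded. *Possibly related*, read equally strictly, needs other cause not excluded and the drug not permanently withdrawn.

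| Type | Other cause | Drug continued | Drug permanently withdrawn |
|---|---|---|---|
| Known | Excluded | Definitely | Definitely |
| Known | Not excluded | Possibly | Neither |
| New | Not excluded | Possibly | Neither |
| New | Excluded | Neither | Neither |

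Combinations that can be drug-related: 1 + 2 = 3 of 4 with the drug continued, and 1 of 4 with the drug withdrawn.

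**Step 3: where the withdrawn cases go.** Split each of the 4 withdrawn combinations by what followed, improvement or a negative or ambiguous reaction: 4 × 2 = 8 profiles.

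- *Definitely*: 2 (known type, other cause excluded, either reaction).
- *Unlikely*: 2 (other cause not excluded, negative or ambiguous reaction, known or new type).
- No category: 8 − 2 − 2 = 4. Three of these are the improving events that miss *Definitely*. The fourth is a new type with other causes excluded and a negative or ambiguous reaction.

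This step takes the last limb of *Not related* to need an actual significant cause. A possible alternative strong enough to qualify could be placed there.

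**Step 4: how open *Definitely related* is in this trial.**

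- Protocol Section 3.5 says pulmonary toxicity, hepatotoxicity and macular edema had not been observed with CBP-307 in prior trials, and Section 7.5 says no eye-related toxicity had been seen. Macular edema that resolves after the mandatory stop is the clearest case: it is hard to call a known reaction to this product, it is barred from *Possibly related*, and it did not react negatively to withdrawal.
- Hepatotoxicity is a weaker example. Sections 3.4.4 and 7.5 report slight ALT rises with CBP-307 in phase I. Bradycardia was also seen, so *Definitely related* can stay open for these.
- The other test is that the event "cannot be explained by other reasons, such as concomitant medications or comorbidities". Subjects have UC, and inclusion criterion 6 concerns treatment with oral 5-ASA or corticosteroids. Alternative explanations will therefore often be available.

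**The case against.** The best defence is that these entries describe typical features for an investigator to weigh. Nothing in Section 8.1.3 says that every sentence of a category must be met. Read that strictly, *Unlikely related* could never apply to an event with the drug continued, because it describes a reaction after withdrawal. The sentence may be a loose rendering of the idea that information on withdrawal or re-administration is lacking.

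This has force as an account of what was probably meant. It does not repair the text. Under *Definitely related* the authors mark withdrawal and restart as an example. Under *Possibly related* the corresponding sentence has no such mark, and neither document relaxes it.

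The objection does bar several stronger inferences:

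- **That every continued-drug combination can be drug-related.** If the withdrawal sentence binds, so does the one before it about other causes, and the new-type, other-cause-excluded event drops out. The count is 3 of 4.
- **That sites are forced to choose *Unlikely* or *Not related*.** An event that fits no category is not thereby placed in one. If the field is left blank, the SAP counts the event as related.
- **That SUSAR reporting is switched off.** All SAEs go to the sponsor or its designee within 24 hours whether related or not. Section 8.2.2 states "Investigator safety reports must be prepared for suspected unexpected serious adverse reactions (SUSARs) according to local regulatory requirements" and adds sponsor policy. It does not make the investigator's label the sole trigger.
- **That withdrawn events disappear.** TEAEs leading to discontinuation, SAEs and AESIs have their own tables without a relationship condition (SAP Sections 15.1.2, 15.1.3 and 15.1.5). AESIs are reported regardless of relationship (Protocol Section 8.3).

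**Conclusion.** The point holds as a defect in a stated rule. Taken as written, Section 8.1.3 does not allow an event followed by permanent withdrawal to be possibly related, and it leaves some events that improve after withdrawal without a category. The size is 1 of 4 definitional combinations against 3 of 4.

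That contrast assumes a literal and even-handed reading. It says nothing about how many events are affected. A reader might infer that most events leading to withdrawal will be missing from the drug-related tables. The documents give no event frequencies or site practice from which to conclude that, and the effect could be nil if investigators use clinical judgement.

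The exposure is confined to the drug-related TEAE tables, the relationship part of the secondary safety endpoint and the investigator's causality label on SAE reports. Safety analyses are descriptive (SAP Section 15), so no planned test is affected. Because the correction is small and specific, it should be made.

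**What to change.** In Protocol Section 8.1.3, delete the sentence from *Possibly related*, or replace it with wording such as: information on withdrawal or re-administration may be lacking, or may support a relationship. Either way, withdrawal or improvement after withdrawal must never bar *Possibly related*. Align any eCRF completion guidance.

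For data already collected, ask investigators to re-check causality for AEs whose recorded action taken is drug withdrawal, the eCRF item that SAP Section 15.1.2 already uses. The re-assessment provision in Section 8.1.3 covers this. For the double-blind parts it is best done while the investigator is still blinded.

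Leave *Definitely related* unchanged. Dropping its known-reaction condition would be a preference about the scale, and the problem does not require it.

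The cost is a one-sentence edit, matching guidance and a limited query round. Slightly more events may be counted as drug-related.

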8.2. Serious adverse event

8.2.1. Definitions of serious adverse events

An SAE is any adverse medical event that meets any of the following criteria at any dose:

- Results in death;
- Life-threatening;
 - Note: "life-threatening" refers to the risk for death in the subject at the time when an event occurs. It does not mean that a more serious event may cause death.
- Hospitalization or prolongation of existing hospitalization is required.

Note: Generally, hospitalization means that due to adverse medical events, subjects receive unscheduled observation and/or treatment (not indicated in outpatient clinics) in the hospital's inpatient department (going through the hospitalization procedure) or emergency wards (usually, subjects need to stay there for at least 24 hours for observation). A complication that

appears during hospitalization is an AE; if the complication prolongs hospitalization or satisfy any other serious criteria, the event is serious. If hospitalization or extended hospital stay is not related to an AE, it is not within the scope of reporting. For example:

- a. Previous illness indicates hospitalization for examination or selective treatment, no new AE occurs, and also, the previous disease does not get worse;
- b. Hospitalization for observation not due to relevant AE, e.g. for social and/or convenience;
- c. Hospitalization required by the study procedure as indicated in the protocol;
- d. Scheduled hospitalization not due to relevant AE, such as scheduled elective surgery;
- Results in persistent or significant disability/incapacity;
- Congenital anomaly or birth defects;
- Important medical events: These AEs may not be immediately life-threatening or result in death, or hospitalization, but may jeopardize the subject and needs intervention to prevent the occurrence of any of the above consequences. These important medical events include intensive treatment in the emergency room or at home for allergic bronchospasm, blood dyscrasias or convulsions that do not result in hospitalization, or drug dependence or drug abuse.

8.2.2. Reporting and follow-up of serious adverse events

SAEs will be collected after subjects sign the informed consent form and throughout the entire study, i.e., until 28 days after the last dose of investigational product.

For any SAEs in the study, whether related to investigational product or not, the investigator should provide timely emergency treatment, and must immediately (within a maximum of 24 hours after becoming aware of the event) inform the sponsor or its designee, and complete the SAE Report Form following specific completion instructions. In the meantime, the investigator should record the SAE in the medical records and eCRF in a timely manner. The investigator must provide causality assessment when reporting SAEs.

Investigator safety reports must be prepared for suspected unexpected serious adverse reactions (SUSARs) according to local regulatory requirements and Sponsor policy and forwarded to Investigators as necessary.

For all SAEs, the investigator needs to conduct follow-up until subjects recover, have stable condition or returns to baseline condition, and provide detailed follow-up information. The timeline and procedure for the follow-up report are the same as the initial report, namely, the investigator should report any follow-up information about the SAEs within 24 hours after awareness.

Regarding follow-up:

- The investigator needs to take appropriate measures to protect the safety of the subject, and it is particularly required that each subject with AEs (abnormal clinical signs, laboratory test results, or others) should be followed up until he/she returns to normal or has stable condition.
- Subjects experiencing SAEs must be followed up until they recover clinically, return to normal or have stable condition. This may require follow-up visits after subjects leave the study and require additional investigation by sponsor.

The original report in written form should be presented in time with details, including a copy of the hospital medical record, a discharge summary, autopsy report (if applicable) and other necessary documents.

8.3. Reporting of adverse events of special interest

In a phase I clinical study on CBP-307 conducted in Australia, potential risk for cardiovascular events was observed in the high-dose group (treated with a dose more than 10 times the therapeutic dose to be administered in this study). Besides, in the post marketing studies of the marketed S1P1 agonist fingolimod and other clinical studies of S1P1 agonists, other potential safety risks were also observed, including pulmonary toxicity, hepatotoxicity, macular edema, severe and opportunistic infections, and skin tumors. Although these potential risks were not observed in the phase I clinical study of CBP-307, special attention is still needed in this study. AEs that require special attention include (see Section 7.5 for detail):

- a. bradycardia and cardiac conduction abnormalities: significant bradycardia (heart rate ≤ 45 beats/min), Mobitz type II or third degree atrioventricular block, and other significant cardiac conduction abnormalities,
- b. pulmonary toxicity: difficulty in breathing and clinically significant wheezing, and
- c. hepatotoxicity: e.g., two consecutive liver function tests in a subject suggesting elevated liver enzymes, AST or ALT > 3 times the ULN, or other clinically significant liver dysfunction.
- d. Macular edema
- e. Opportunistic infection or severe infection: tuberculosis, serious bacterial infections, systemic fungal infections, viral infections such as herpes infections (including herpes zoster and disseminated herpes simplex) and protozoal infections.
- f. Malignant neoplasm of skin

All AEs of special interest specified in the protocol (see Section 7.5) have to be reported to sponsor and CRO, regardless of seriousness and relationship to the investigational product.

- For events conforming to the requirements of SAE, report according to expedited reporting procedures for SAE (see Section 8.2);
- Regarding an event that does not meet the criteria for a SAE, it is only needed to be recorded in the eCRF.

